Assessment of pregnancy for women of childbearing potential: method of assessment per physician discretion	Retain at site
Documentation of: 
 Demographics: age at implant, gender, race, ethnicity Indication for implant Cardiovascular medications Subject's height and weight Arrhythmia history Cardiac disease history 	Retain at site
Implant details regarding IPG, leads, and accessories used or signed Implant Technical Source Form	Retain at site
Printout of PSA measurements and ECG strip showing loss of capture or signed Implant Technical Source Form	Retain at site
Implant questionnaire	Retain at site
For in-clinic visits: Printout of IPG measurements and threshold results (device follow-up report and ECG programmer strip documenting LOC), for all lead pacing threshold tests	Retain at site
For remote visits: Appropriate LATITUDE report or page print of LATITUDE data or signed Technical Source Form for IPG measurements and threshold results	Retain at site
Time of pocket closure, to document time 0	Retain at site
Time of pre-discharge visit to document visit window	Retain at site
PA and lateral chest X-ray or fluoroscopic image of lead distal tip fixation, either from Implant or Pre-Discharge	Retain at site
Reportable Adverse Events, Device Deficiencies, and Protocol Deviations, if applicable	Retain at site
In the event of subject death: 
 Death narrative Relevant medical records Death certificate Autopsy report 	Submit one copy to Boston Scientific RM At [contact] or uploaded to the Rave Database Retain at site

Note: If thermal paper from the device programmer is used for source documentation, signed and dated photocopies or printed pdfs should be used instead, or the strips should be electronically saved.

11. Statistical Considerations

11.1. *Endpoints*

For an INGEVITY+ lead to be eligible to contribute to endpoint analyses, it must be the final lead implanted or attempted per chamber during the initial procedure. Therefore, each subject may contribute up to two total INGEVITY+ leads to the endpoint analyses – one each for the right atrium and right ventricle. See section 11.3.1 for specifics on the analysis sets used for each endpoint analysis.

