11.1.1. Primary Safety Endpoint: Lead-related Complication-Free Rate from 0 to 3 Months

Safety of the INGEVITY+ Leads will be confirmed by the lead-related complication-free rate (CFR) from lead implant through the three-month follow-up, based on complications that are related to the INGEVITY+ Lead. Lead-related complications are defined as lead-related adverse events resulting in permanent loss of pacing therapy, invasive intervention, injury, or death. Lead-related adverse events include, but are not limited to the following, based on the Advamed Industry Guidance for Uniform Reporting of Clinical Performance of Cardiac Rhythm Management of Pulse Generators and Leads¹, and in accordance with the FDA Guidance²:

- Cardiac perforation requiring surgical intervention
- Cardiac perforation not requiring surgical intervention
- Conductor fracture/ helix damage
- Lead dislodgment
- Failure to capture
- Oversensing
- Failure to sense (undersensing)
- Insulation breach
- Abnormal pacing impedance
- Extracardiac stimulation

Lead-related complications associated with attempted INGEVITY+ Lead implants will count toward this safety endpoint. Lead-related adverse events that are not a complication will be counted as a complication if intravenous (IV) drug therapy is necessary to treat the event. IV drug therapy that occurs concomitant but unrelated to the lead-related adverse event will not be counted as a lead-related complication. Complications involving an INGEVITY+ lead that occur as a result of a procedure unrelated to that INGEVITY+ lead will not count toward this safety endpoint. Two examples of this scenario are 1) an INGEVITY+ lead dislodgement resulting from an ablation procedure and 2) an RV INGEVITY+ lead dislodgement resulting from a repositioning of an RA lead (INGEVITY+ or other market-released).

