11.1.1.3. Statistical Methods

Data from all implanted or attempted leads at the time of endpoint analysis will be eligible for inclusion in the endpoint analysis.

The lead-related complication-free rate from date of implant (or date of attempt, for leads attempted but not implanted) through 91 days post-implant will be calculated using Kaplan-Meier methodology. The 97.5% one-sided lower pointwise confidence limit of the complication-free rate will be calculated via log-log methodology for all eligible leads contributing to the analysis and compared to the performance goal of 93%. If the lower confidence limit exceeds 93%, the null hypothesis will be rejected.

Each lead's exact follow-up time in the 91-day post-implant period will be included in the analysis via Kaplan-Meier methodology. The leads that fail to reach 91 days of follow-up (without experiencing an endpoint event prior to their end of follow-up in the period) will be censored at the time of their end of follow-up in the period. Because non-informative censoring cannot be assumed for these leads, a tipping point analysis will be performed to determine the potential effects these censored leads could have on the results if full information on each lead was present. The tipping point analysis will assign each lead that was censored prior to 91 days as either having or not having an endpoint event. All possible combinations of these leads' data will be evaluated along with the actual observed data to find the point, if any, at which the endpoint is failed. An exact binomial test will be performed for the tipping point analysis.

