11.1.4.1. Hypotheses

The following hypotheses will be used to evaluate Effectiveness Endpoint 3 for each of the lead fixation types:

$$H_0: \text{Pacing impedance} \leq 300 \Omega, \text{ or Pacing impedance} \geq 1300 \Omega$$

$$H_a: 300 \Omega < \text{Pacing impedance} < 1300 \Omega$$

11.1.4.2. Sample Size for Secondary Effectiveness Endpoint 2

A sample size of 15 leads (13 required for analysis plus 2 for attrition) is required for Effectiveness Endpoint 3. This sample size was calculated using a one-sample t-test, using SAS version 9.4 with the following assumptions:

- Expected performance = $650 \pm 400 \Omega$
- Performance goals = 300Ω and 1300Ω
- Expected attrition/missing data = 10%
- One-sided significance level = 5%
- Power = 90%

Note that the sample size for the study is not determined by this endpoint.

11.1.4.3. Statistical Methods for Secondary Effectiveness Endpoint 2

All pacing impedance data collected at the three-month follow-up visit that is available at the time of analysis will be included in the endpoint analysis.

Two one-sided t-tests (TOST) will be performed, using an alpha equal to 5% for each test. If the TOST is deemed to be inappropriate based on the data, a data transformation or a non-parametric test will be performed. If both of the p-values for the two one-sided tests are less than 0.05, the null hypothesis will be rejected.

11.2. *Ancillary Analysis*

- Summary of turn count for all implanted and attempted leads
- Summary of the implant questionnaire including:
 - Lead handling
 - Lead maneuverability
- Summary of accessories used

- Summary of lead-related Adverse Events
- Summary of lead-related device deficiencies, including extension/retraction issues

11.3. ***General Statistical Methods***

11.3.1. **Analysis Sets**

For an INGEVITY+ lead to be eligible to contribute to endpoint analyses, it must be the final lead implanted or attempted per chamber during the initial procedure. Therefore, each subject may contribute up to two total INGEVITY+ leads to the endpoint analyses – one each for the right atrium and right ventricle. These leads will be called ‘endpoint leads’ in this section. The following analysis sets will be used for each endpoint.

Endpoint	Analysis Sets
Primary Safety Endpoint	All endpoint leads
Primary Efficacy Endpoint	All endpoint leads with 3-month visit PCT data
Secondary Efficacy Endpoint 1	All implanted endpoint leads with 3-month visit sensed amplitude measurements

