11.4.5. Impact of Repeated Measures

As stated in Section 11.3.1, each subject in the study can contribute up to two leads to the endpoint analyses. To investigate the potential impact of repeated measures on the endpoint

results, analyses will be performed for each primary endpoint comparing a model adjusted for repeated measures to one unadjusted for repeated measures. Results from both models – accounting and not accounting for repeated measures – will be presented.

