- Hemothorax
- Inability to pace
- Inappropriate therapy (e.g., shocks and antitachycardia pacing [ATP] where applicable, pacing)
- Incisional pain
- Incomplete lead connection with pulse generator
- Infection including endocarditis
- Lead dislodgment
- Lead fracture
- Lead insulation breakage or abrasion
- Lead tip deformation and/or breakage
- Malignancy or skin burn due to fluoroscopic radiation
- Myocardial trauma (e.g., tissue damage, valve damage)
- Myopotential sensing
- Oversensing/undersensing
- Pericardial rub, effusion
- Pneumothorax
- Pulse generator and/or lead migration
- Syncope
- Tachyarrhythmias, which include acceleration of arrhythmias and early, recurrent atrial fibrillation
- Thrombosis/thromboemboli
- Valve damage

- Vasovagal response
- Venous occlusion
- Venous trauma (e.g., perforation, dissection, erosion)

For a list of potential adverse events associated with MRI scanning, refer to the appropriate ImageReady MR Conditional Pacing System or Defibrillation System MRI Technical Guide.

16.3. *Risk Minimization Actions*

Additional risks may exist. Risks can be minimized through compliance with this protocol, performing procedures in the appropriate hospital environment, adherence to subject selection criteria, close monitoring of the subject's physiologic status during research procedures and/or follow-ups and by promptly supplying BSC with all pertinent information required by this protocol.

16.4. *Anticipated Benefits*

Subjects enrolled in this clinical study may not receive any direct benefit from their participation; however, medical science and future patients may benefit from their participation in this clinical study.

The potential benefits the subject may receive from the INGEVITY+ Lead would be the same if they did not enroll in this study.

17. Safety Reporting

17.1. *Reportable Events by investigational site to Boston Scientific*

It is the responsibility of the investigator to assess and report to BSC any event which occurs in any of following categories:

- All Serious Adverse Events
- All Device Deficiencies
- Unanticipated Adverse Device Effects/Unanticipated Serious Adverse Device Effects
- All INGEVITY+ Lead Related Adverse Events
- All Cardiac Related Adverse Events
- All INGEVITY+ Lead Procedure Related Adverse Events

When possible, the medical diagnosis should be reported as the Event Term instead of individual symptoms.

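### The final-lead-per-chamber rule leaves complications of INGEVITY+ leads exchanged at implant out of the primary safety test, and no planned sensitivity analysis brings them back

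*Combined protocol and SAP*

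**What the plan says.** Section 11.1 sets the entry condition for every endpoint: to be eligible a lead must satisfy "it must be the final lead implanted or attempted per chamber during the initial procedure". This gives at most one right atrial and one right ventricular lead per subject. Section 11.1 then sends the reader on: "See section 11.3.1 for specifics on the analysis sets used for each endpoint analysis". Section 11.3.1 repeats the condition, calls the qualifying leads endpoint leads, and makes all of them the primary safety set. Section 11.4.5 relies on the same limit: "As stated in Section 11.3.1, each subject in the study can contribute up to two leads to the endpoint analyses".

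Two passages on the primary safety endpoint use wider wording. Section 11.1.1 states: "Lead-related complications associated with attempted INGEVITY+ Lead implants will count toward this safety endpoint". Section 11.1.1.3 states: "Data from all implanted or attempted leads at the time of endpoint analysis will be eligible for inclusion in the endpoint analysis". Neither mentions the final-lead condition. Section 11.1.1.3 also starts follow-up at the date of attempt for a lead that was attempted but not implanted.

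The only missing-data sensitivity analysis for safety is a tipping-point analysis restricted to censored leads: "The tipping point analysis will assign each lead that was censored prior to 91 days". Elsewhere, 11.2 plans a "Summary of lead-related Adverse Events", 17.1 makes "All INGEVITY+ Lead Related Adverse Events" reportable, and 10.5 collects data on every lead attempted as well as every lead implanted.

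**The concern.** Suppose the first INGEVITY+ lead placed in a chamber perforates, the event meets the complication definition (for example through injury or an invasive intervention), and the operator exchanges it for a second INGEVITY+ lead in that chamber. The first lead is not the final one, so under 11.3.1 it is not in the safety set. Nothing in the plan moves its event to the replacement lead, the chamber or the subject. The replacement lead enters as event-free unless it has a complication of its own.

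Two things are at stake. First, a reader of 11.1.1 and 11.1.1.3 alone could expect the event to be in the test, while a reader of 11.3.1 would leave it out. Second, the study concerns a lead redesigned for helix extension and retraction during implantation (4.1), and 7.3 expects any effect of the changes in short-term use. Complications at the implant attempt are therefore directly relevant to the safety question.

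The concern is limited to events that meet the complication definition or the intravenous-drug rule in 11.1.1. An exchange or a difficult helix is not in itself an endpoint event, since 17.5 says that device deficiencies are not adverse events. Exchange to a lead from another family is outside this point.

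**Working it through.** **1. Can the texts be reconciled, and what follows?**

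| Section | Leads or events covered | Final-lead limit stated? |
|---|---|---|
| 11.1, 11.3.1 | Final INGEVITY+ lead implanted or attempted, per chamber | Yes |
| 11.4.5 | At most two leads per subject | By reference to 11.3.1 |
| 11.1.1 | Complications of attempted implants | No |
| 11.1.1.3 | All implanted or attempted leads | No |

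The final-lead rule itself covers attempted leads, so the attempted leads of 11.1.1 and 11.1.1.3 can be read as final leads that were attempted but not implanted. That reading is consistent, and it settles that the exchanged lead's complication is outside the test. The Attempt class in 9.4 does not bring it back: it covers subjects who end without an INGEVITY+ lead, whereas a subject with a successful exchange is an Implant subject.

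**2. Does any other planned analysis recover the event?** No. The tipping-point analysis reassigns only leads censored before 91 days, and the repeated-measures models in 11.4.5 use the same endpoint leads. The summary in 11.2 describes the event without testing it.

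**3. The plan's own sample size.** Inputs from 11.1.1.2: p0 = 0.93, p1 = 0.98, one-sided 2.5%, power 90%, attrition 7.5%.

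n = [(1.960·√(0.93·0.07) + 1.2816·√(0.98·0.02)) / 0.05]² = 184.7, rounded up to 185; 185/0.925 = 200. Both stated figures reproduce.

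**4. How many events can the test tolerate?** With no censoring and x events in n leads, S = 1 − x/n, se = √((1−S)/(n·S))/|ln S|, and the log-log lower limit is S^exp(1.96·se).

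| Leads | Events | S | se | Lower limit | Against 93% |
|---|---|---|---|---|---|
| 200 | 6 | 0.9700 | 0.4083 | 93.44% | pass |
| 200 | 7 | 0.9650 | 0.3780 | 92.80% | fail |
| 185 | 5 | 0.9730 | 0.4472 | 93.63% | pass |
| 185 | 6 | 0.9676 | 0.4083 | 92.92% | fail |

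One omitted event can therefore decide the result. If 6 events are counted on 200 endpoint leads and one more sits on an exchanged lead, adding it gives 92.80% when scored on the chamber and 92.83% when the exchanged lead is added as a 201st lead. Both fail.

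**5. Is the direction fixed?** Against a per-chamber count it is: leaving an event out can only raise the complication-free rate. Against a literal count of all attempted leads it is not, because event-free exchanged leads also enlarge the denominator. Seven events fail at 200 leads (92.80%) but pass at 206 (93.005%); six fail at 185 (92.92%) but pass at 188 (93.03%).

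**6. Effect on the chance of a wrong pass.** Let f be the share of qualifying complications that fall on exchanged leads. The documents give no value, so f is an assumed range. With a true per-chamber rate of exactly 93%, P(pass) = P(Bin(n, 0.07·(1−f)) ≤ c), with c = 6 at 200 leads and c = 5 at 185.

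| f | 200 leads | 185 leads |
|---|---|---|
| 0 | 1.2% | 0.9% |
| 5% | 1.9% | 1.4% |
| 10% | 2.9% | 2.2% |
| 20% | 6.5% | 5.0% |

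P(pass) reaches 2.5% at f ≈ 8.4% (200 leads) or f ≈ 11.5% (185 leads). The calculation treats leads as independent and follow-up as complete.

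**The case against.** The strongest reply is that the plan does not contradict itself. The general rule already covers leads implanted or attempted, 11.1 says what makes a lead eligible, and a later subsection need not repeat it. This stands. A reader might infer that the plan promises in 11.1.1 to count these events and then breaks the promise in 11.3.1. The documents do not support that, because on the harmonised reading 11.1.1 makes no promise about non-final leads. What remains is that the harmonised rule leaves the event out of the test and the plan never says so plainly.

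A second reply concerns the benchmark. The 93% goal is the average of earlier lead studies less 5 points (11.1.1.1), and the revision history says the endpoint was designed for comparability with other lead studies. If those studies used a final-lead rule, a different count here would break the comparison. This also stands: the documents do not say how those studies counted exchanged leads, so they do not show that the comparison is biased or that one count must be primary.

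A third reply concerns size. The shares f have no source. One could also cite the chance, at a true 98%, that the exclusion turns a per-chamber failure into a pass: 2.0, 3.7 or 6.5% with 200 leads for f = 5, 10 or 20%. A reader might take those as wrong conclusions. They are not, because at 98% the lead truly meets the goal and the exclusion only avoids a false failure. At 98% with 200 leads, 4 complications are expected (0.02 × 200), so f = 10% means 0.4 of an event in the whole study. The 185-lead figures also overstate fragility somewhat, since the Kaplan-Meier estimate uses the follow-up of censored leads too.

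Last, the events are reportable, summarised and reviewed during the study, and 11.4.6 requires changes made before analysis to be documented in an approved SAP. These safeguards keep the event visible, but they do not put it in the test.

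**Conclusion.** The point holds as a gap in the primary safety analysis. Read consistently, the plan excludes a qualifying complication of an exchanged, non-final INGEVITY+ lead from the hypothesis test, and no planned sensitivity analysis shows what that exclusion does.

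Its size is unknown, and zero if no exchanged lead has a qualifying event. It matters only near the pass limit, where a single event decides. Because the test is conservative at these sample sizes, the exclusion takes the wrong-pass probability above 2.5% only beyond the shares of about 8.4% or 11.5% found above. These figures assume complete follow-up, independent leads and a per-chamber comparator that the plan itself does not specify. Severity: minor.

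**What to change.** Before analysis, reconcile 11.1, 11.1.1, 11.1.1.3 and 11.3.1 so that they say the same thing about non-final attempted leads. For the primary safety endpoint only, pre-specify two analyses:

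- **Per-chamber count.** A qualifying lead-related complication of any INGEVITY+ lead attempted in a chamber at the initial procedure counts against that chamber, with at most two units per subject.
- **Final-lead count.** The current 11.3.1 set, unchanged.

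The sponsor should state in advance which is primary, according to how the studies behind the 93% goal counted exchanged leads, and report the other as a sensitivity analysis. Fixing this early is preferable because 11.4.1 has adverse events analysed at frequent intervals during the study. Report the number of exchanged INGEVITY+ leads and the qualifying events on them. Keep the final-lead rule for the 3-month electrical endpoints, where only the lead left in place can be measured.

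The cost is some wording and one extra analysis, and 10.5 and 17.1 already provide the data. The downside is that the per-chamber rate may be slightly less favourable. If it is made primary without knowing how the benchmark studies counted, it may also be less comparable with them.

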11.1.1. Primary Safety Endpoint: Lead-related Complication-Free Rate from 0 to 3 Months

Safety of the INGEVITY+ Leads will be confirmed by the lead-related complication-free rate (CFR) from lead implant through the three-month follow-up, based on complications that are related to the INGEVITY+ Lead. Lead-related complications are defined as lead-related adverse events resulting in permanent loss of pacing therapy, invasive intervention, injury, or death. Lead-related adverse events include, but are not limited to the following, based on the Advamed Industry Guidance for Uniform Reporting of Clinical Performance of Cardiac Rhythm Management of Pulse Generators and Leads¹, and in accordance with the FDA Guidance²:

- Cardiac perforation requiring surgical intervention
- Cardiac perforation not requiring surgical intervention
- Conductor fracture/ helix damage
- Lead dislodgment
- Failure to capture
- Oversensing
- Failure to sense (undersensing)
- Insulation breach
- Abnormal pacing impedance
- Extracardiac stimulation

Lead-related complications associated with attempted INGEVITY+ Lead implants will count toward this safety endpoint. Lead-related adverse events that are not a complication will be counted as a complication if intravenous (IV) drug therapy is necessary to treat the event. IV drug therapy that occurs concomitant but unrelated to the lead-related adverse event will not be counted as a lead-related complication. Complications involving an INGEVITY+ lead that occur as a result of a procedure unrelated to that INGEVITY+ lead will not count toward this safety endpoint. Two examples of this scenario are 1) an INGEVITY+ lead dislodgement resulting from an ablation procedure and 2) an RV INGEVITY+ lead dislodgement resulting from a repositioning of an RA lead (INGEVITY+ or other market-released).

11.1.1.1. Hypotheses

The following hypotheses will be used to evaluate Primary Safety Endpoint:

H_0 : The lead-related complication-free rate from 0 to 3 months $\leq 93\%$

H_a: The lead-related complication-free rate from 0 to 3 months > 93%

The performance goal was selected to ensure that the INGEVITY+ Lead has a similar safety profile in the implant through 3-month post-implant period as other market-approved pace/sense leads in the same period. The average of the complication-free rates observed in studies used to support market approval of various pace/sense leads was used to establish average market-approved lead safety. A clinically acceptable delta of 5% was then subtracted from this average of 98% to establish the performance goal of 93%.

